#### **PET Imaging days**

The 2 PET imaging procedures will be done at least 14 days apart. The day of the first PET imaging agent injection will be considered study Day 1. Please refer to the study protocol Section 8.3.1 for the steps that will take place on each PET imaging day.

Both visits will also be considered as the End of Treatment (EOT) visits.

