#### Study day

The study day describes the day of the event or assessment date, relative to the reference start date.

The study day is defined as:

- The date of the event (visit date, onset date of an event, assessment date etc.) reference start date + 1 if event is on or after the reference start date;
- The date of the event (visit date, onset date of an event, assessment date etc.) reference start date if event precedes the reference start date.

The reference date for all assessments (safety, efficacy, etc) is the start of study treatment.

The study day will be displayed in the data listings. If an event starts before the reference start date, the study day displayed on the listing will be negative.

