#### Windows for multiple assessments

In order to summarize weight, vital signs, and laboratory tests collected over time (including unscheduled visits), the assessments will be time slotted. The following general rule will be applied in creating the assessment windows: If more than one assessment is done within the same time window, the assessment performed closest to the target date will be used. If 2 assessments within a time window are equidistant from the target date, then the earlier of the 2 assessments will be used. If there are multiple assessments on the same date then the worst case value will be used. Data from all assessments (scheduled and unscheduled), including multiple assessments, will be listed.

For participants randomized into sequence 1: [18F]CTT1057 - [68Ga]Ga-PSMA-11

Time Window	Planned Visit Timing	Time Window Definition
On treatment		
Baseline for [18F]CTT1057	On or before Study Day 1*	≤ Study Day 1, and time prior to [  F]CTT1057 injection
Day 1 for [18F]CTT1057	Study Day 1	Date of [18F]CTT1057 injection
Day 15 for PET for [18F]CTT1057	Study Day 15	Study Day 15 - 22, and time prior to [  Ga]Ga-PSMA-11 injection
Baseline (Day 1) for [68Ga]Ga-PSMA-11	On or before [  Ga]Ga-PSMA-11 injection and after [  F]CTT1057 injection	≥Study Day 15 and ≤ Study Day 22, time prior to [  Ga]Ga-PSMA-11 injection
Day 1 for [  Ga]Ga- PSMA-11	On [  Ga]Ga-PSMA-11 injection	Date of [  Ga]Ga-PSMA-11 injection

\*Study Day 1 = the date of [18F]CTT1057 injection

For participants randomized into sequence 2: [68Ga]Ga-PSMA-11 - [18F]CTT1057

Time Window	Planned Visit Timing	Time Window Definition	
On treatment			
Baseline for [  Ga]Ga- PSMA-11	On or before Study Day 1*	≤ Study Day 1, and time prior to [  Ga]Ga-PSMA-11 injection	
Day 1 for [  Ga]Ga- PSMA-11	Study Day 1	Date of [  Ga]Ga-PSMA- 11injection	
Day 15 for PET for [  Ga]Ga-PSMA-11	Study Day 15	Study Day 15 - 22, time prior to [  F]CTT1057 injection	
Baseline for [18F]CTT1057	On or before [  F]CTT1057 and after [  Ga]Ga-PSMA-11	≥Study Day 15 and ≤ Study Day 22, time prior to [18F]CTT1057 injection	
Day 1 for [18F]CTT1057	On [18F]CTT1057 injection	Date of [  F]CTT1057 injection	
Day 15 for [18F]CTT1057	the date of [18F]CTT1057 injection + 14 days	Study Day 29-39	

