\*Study Day 1 = the date of [68Ga]Ga-PSMA-11 injection

For vital signs, post-injection/pre-imaging, and post-imaging assessment will be compared to the baseline (pre-injection assessment) in addition to its Day 15 assessment compared to baseline. Post-injection/pre-imaging and post-imaging will be performed on the day of imaging.

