### 2.7.1 Adverse events (AEs)

Adverse events are coded using MedDRA terminology. The latest MedDRA version used for reporting will be specified in the CSR and as a footnote in the applicable tables/listings. AEs will be assessed according to the Common Terminology Criteria for Adverse Events (CTCAE) version 5.0. Summary tables for adverse events (AEs) will include only AEs that started or worsened during the on-treatment period (see Section 2.1.1). All AEs that started or worsened within 14 days after the [F]CTT1057 dose and as long as they were prior to the [Ga]Ga-

PSMA-11 dose (applicable for Sequence 1), and adverse events that were reported as related to [F]CTT1057 irrespective of time of onset will be regarded as [F]CTT1057 **treatment-emergent** AEs. Similarly, all AEs that started or worsened within 14 days after the [Ga]Ga-PSMA-11 dose and as long as they were prior to the [F]CTT1057 dose (applicable for Sequence 2), and adverse events that were reported as related to [Ga]Ga-PSMA-11 irrespective of time of onset will be regarded as [Ga]Ga-PSMA-11 **treatment-emergent** AEs. [F]CTT1057 TEAEs and [Ga]Ga-PSMA-11 TEAEs will be summarized.

AEs will be summarized by the number and percentage of participants having at least one AE, having at least one AE in each primary system organ class (SOC) and for each preferred term (PT) using MedDRA coding. A participant with multiple occurrences of an AE will be counted only once in the respective AE category. A participant with multiple CTCAE grades for the same preferred term will be summarized under the maximum CTCAE grade recorded for the event. AE with missing CTCAE grade will be included in the 'All grades' column of the summary tables.

In AE summaries, the primary system organ class will be presented alphabetically and the preferred terms will be sorted within primary SOC in descending frequency.

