# 5.1.2 AE, ConMeds and safety assessment date imputation

Table 5-1 Imputation of start dates (AE, CM) and assessments (LB, EG, VS)

Missing	Rule
Element	
day, month, and year	No imputation will be done for completely missing dates
day, month	
 
If available year = year of study treatment start date then         
 
If stop date contains a full date and stop date is earlier than study treatment start date then set start date = 01JanYYYY
 
Else set start date = study treatment start date.
 
 
 
If available year > year of study treatment start date then 01JanYYYY
 
If available year < year of study treatment start date then 01JulYYYY
 

Missing	Rule
Element	
day	
 
If available month and year = month and year of study treatment start date then
 
If stop date contains a full date and stop date is earlier than study treatment start date then set start date= 01MONYYYY.
 
Else set start date = study treatment start date.
 

	
 
If available month and year > month and year of study treatment start date then 01MONYYYY
 
If available month and year < month year of study treatment start date then 15MONYYYY
 

Table 5-2 Imputation of end dates (AE, CM)

Missing	Rule	
Element	(*=last study treatment date plus 15 days not > (death date, cut-off date,	
	withdrawal of consent date))	
day, month, and year	• Completely missing end dates (incl. ongoing events) will be imputed by the end date of the on-treatment period*	
day, month	• If partial end date contains year only, set end date = earliest of 31DecYYYY or end date of the on-treatment period *	
day	• If partial end date contains month and year, set end date = earliest of last day of the month or end date of the on-treatment period*	

If imputed end date < start date, set end date = start date.

Any AEs and ConMeds with partial/missing dates will be displayed as such in the data listings.

Any AEs and ConMeds which are continuing as per data cut-off will be shown as 'ongoing' rather than the end date provided.

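### SAP Table 5-1 imputes partial AE start dates from the first injection only, so most partially dated AEs that follow the second tracer are not counted for it and the per-tracer TEAE tables are mixed (minor)

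*SAP*

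**What the plan says.** SAP 5.1.2, Table 5-1, imputes partial AE start dates by comparing them with the study treatment start date. If only the day is missing, two branches matter here:

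- Same month and year as the anchor, and no full stop date before the anchor: "Else set start date = study treatment start date".
- Later month: the branch reads "month and year of study treatment start date then 01MONYYYY", that is, the 1st of the AE month.

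No branch refers to the second injection.

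Table 5-1 does not define its anchor. SAP 2.1.1 (Study day) does: "The reference date for all assessments (safety, efficacy, etc) is the start of study treatment". SAP 1.1 adds: "The day of the first PET imaging agent injection will be considered study Day 1". For Sequence 2 the window table carries the note "Study Day 1 = the date of [68Ga]Ga-PSMA-11 injection".

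SAP 2.7.1 states: "Summary tables for adverse events (AEs) will include only AEs that started or worsened during the on-treatment period". An AE belongs to a tracer if it began or worsened within 14 days after that tracer and before the other tracer's dose. AEs reported as related to a tracer count for that tracer whatever their onset date. SAP 2.7 presents the safety tables for the F-SAF and Ga-SAF separately.

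**The concern.** The safety endpoint in SAP Table 1-1 is the TEAE rate within 14 days of each tracer. For an AE not reported as related, the onset date relative to both injections decides which tracer it is counted under. An imputation rule that knows only the first injection cannot make that decision for a partial date. It pulls the AE back to the first injection or to the start of the calendar month, and both usually precede the second injection.

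Protocol 4.1 separates the scans by at least two weeks so that each tracer's safety profile can be read cleanly. For AEs with a partial start date, the rule undoes that separation.

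**Working it through.** The plan states no figure on this point, so there is none to reproduce.

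**Inputs from the documents.** First injection at t1, second at t2 = t1 + g. The minimum gap is 14 days (SAP 1.1: "The 2 PET imaging procedures will be done at least 14 days apart"). The SAP 2.1.1 window for the second tracer's baseline, in Sequence 2 "≥Study Day 15 and ≤ Study Day 22, time prior to [18F]CTT1057 injection", gives g = 14 to 21.

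**Assumptions not in the documents.** Only the day is missing; true onset is t2 + l, with l uniform on 0 to 14 days; t1 is uniform over a four-year calendar (1461 days, 48 of them the 1st of a month); g is uniform where averaged; any stop date is not before t1; the AE is not reported as related to either tracer.

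**Step 1: still counted for the second tracer.** The imputed date is on or after t2 only if a 1st of the month falls on one of the l + 1 days from t2 to t2 + l. The probability is (l + 1) × 48/1461. The mean of l + 1 over l = 0 to 14 is 8, so the share is 8 × 48/1461 = 384/1461 = 26.3%, whatever the gap. The share lost to the second tracer is 100 − 26.3 = 73.7%.

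**Step 2: counted for neither.** The 1st of the month must fall after t1 + 14 and before t2. That leaves g − 15 days (none at g = 14 or 15).
- g = 21: 6 × 48/1461 = 19.7%.
- Average over g = 14 to 21: (0+0+1+2+3+4+5+6)/8 = 2.625 days; 2.625 × 48/1461 = 8.6%.

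**Step 3: counted for the first tracer.** This is the remainder.

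| Gap | First | Neither | Second |
|---|---|---|---|
| 14 days | 73.7% | 0% | 26.3% |
| 14-21 days | 65.1% | 8.6% | 26.3% |
| 21 days | 54.0% | 19.7% | 26.3% |

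Enumerating every calendar date gives the same figures. Of the 65.1%, 20.3 points come from the same-month branch and 44.8 from the 1st-of-month branch, so both branches need correction.

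**Step 4: the reverse direction.** An AE that follows the first tracer and precedes t2 is imputed either to t1 or to the 1st of a later month. That 1st lies between t1 and the true onset. Both dates stay in the first tracer's window, so 0% move to the second.

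**Step 5: sensitivity.**
- Onset lag, gap 14-21 days: share to the first tracer 88.1% for same-day onset, 83.2% for days 0-3, 53.6% for days 7-14.
- Assumed gap of 28 days, outside the scheduled window: 31.0% first, 42.7% neither, 26.3% second.
- Day and month both missing, gap 14-21 days: 97.1% first, 0.7% neither, 2.2% second.

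**Examples, Sequence 2** ([68Ga]Ga-PSMA-11, then [18F]CTT1057):
- Injections 3 and 17 March, true onset 20 March: imputed 3 March, counted for [68Ga]Ga-PSMA-11.
- Injections 20 March and 5 April, true onset 8 April: imputed 1 April, counted for [68Ga]Ga-PSMA-11.
- Injections 14 March and 4 April, true onset 8 April: imputed 1 April, 18 days after the first injection and before the second, counted for neither.
- Injections 10 and 25 March, true onset 3 April: imputed 1 April, counted correctly for [18F]CTT1057.

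**The case against.** **The anchor may be meant per tracer.** SAP 2.1.1 defines the safety baseline from the start of each tracer separately, and the safety tables are built by tracer. With an anchor for each tracer, a second-tracer AE would be dated to that injection, or to a 1st of the month between injection and onset, and the loss would be 0%. But Table 5-1 does not say so. SAP 2.1.1 gives one reference date for all assessments, and where the SAP means a tracer-specific start it names the tracer. Table 5-2 uses the separate term last study treatment date, which also suggests that Table 5-1 means the first. The objection shows that the remedy is easy; it does not make the written rule correct.

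**The set at risk is small.** This stands. AEs are sought by telephone 24-72 hours after each scan and at visits near Days 15 and 29, start and end dates are to be recorded, and missing values are queried. AEs reported as related are protected from the date rule. Listings show partial dates as collected. The endpoint is secondary and descriptive.

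**The error has no single direction overall.** This also stands. A reader who looks only at Sequence 2 might infer that the reported [18F]CTT1057 TEAE rate is understated. The documents do not support that. In Sequence 1 the same rule moves [68Ga]Ga-PSMA-11 AEs to [18F]CTT1057; allocation is 1:1; and the AE tables are not stated to be split by sequence.

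**Conclusion.** The point holds as a minor error in the imputation rule. Read with SAP 2.1.1, Table 5-1 fails to count about 74% of second-tracer AEs with a missing start day for that tracer. Over the scheduled gap, 54-74% go to the first tracer and 0-20% to neither, and none move the other way. This removes non-related AEs from [18F]CTT1057 in Sequence 2 and adds [68Ga]Ga-PSMA-11 AEs to it in Sequence 1. Errors that partly offset in the pooled F-SAF do not make either per-tracer rate right.

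The percentages rest on uniform calendar dates and onset lags. They are shares of the partially dated, non-related AEs only. The documents give no count of these, so the absolute effect on the TEAE rates cannot be sized.

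**What to change.** In SAP 5.1.2, define the anchor for each tracer and replace the single-anchor rule for partial start dates along these lines: for each tracer received, count the AE as a TEAE of that tracer if any date compatible with the partial start date, and not after the stop date where one is known, falls within 14 days after that tracer and before the other tracer's dose where that dose came later. Keep the existing rule for related AEs. Apply the same rule to concomitant medications, which SAP 2.4.2 assigns with the same per-tracer windows.

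Do not instead set the onset to the [18F]CTT1057 injection whenever that date lies in the AE's month. That creates the reverse error in Sequence 2 and leaves the mixing in Sequence 1. A comparable rule, taking the latest injection in the known month, moves about 65% of first-tracer AEs with a missing day to the second tracer when no stop date excludes it.

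The cost is a few lines of SAP text and a change to the imputation code. A few AEs will be counted under both tracers; a footnote giving their number would make this visible.

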## 5.1.3 Other imputations

For incomplete date of initial diagnosis of cancer and date of biochemical recurrence diagnosis missing day is defaulted to the 15th of the month and missing month and day is defaulted to 01-Jan.

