5.1 Inclusion criteria

Participants eligible for inclusion in this study must meet all of the following criteria:

- 1. Signed informed consent must be obtained prior to participation in the study
- 2. Biopsy proven prostate adenocarcinoma.

3a. Biochemical recurrence following initial definitive therapy (with either RP or curative intent radiation therapy) as defined:

- by AUA criteria (Cookson et al 2007) for patients who have undergone RP: Initial serum PSA of ≥0.2 ng/ml measured at least 6 weeks after RP with a second confirmatory persistent PSA level of >0.2 ng/ml, or
- by ASTRO-Phoenix criteria (Roach et al 2006) for patients who have undergone curative-intent radiation therapy (RT): Rise of serum PSA measurement of 2 or more ng/mL above the nadir PSA observed post RT.
- 4. ECOG performance status 0-2
- 5. Participants must be adults ≥ 18 years of age

5.2 **Exclusion criteria**

Participants meeting any of the following criteria are not eligible for inclusion in this study.

- 1. Inability to complete the needed investigational and standard-of-care imaging examinations due to any reason (severe claustrophobia, inability to lie still for the entire imaging time, etc.)
- 2. Any additional medical condition, serious intercurrent illness, concomitant cancer or other extenuating circumstance that, in the opinion of the Investigator, would indicate a significant risk to safety or impair study participation, including, but not limited to, current severe urinary incontinence, hydronephrosis, severe voiding dysfunction, need of indwelling/condom catheters, New York Heart Association class III or IV congestive heart failure, history of congenital prolonged QT syndrome, uncontrolled infection, active hepatitis B or C, and COVID-19
- 3. Prior major surgery undergone less than 12 weeks prior to screening (with the exception of any surgery related to prostatic cancer)
- 4. Known allergy, hypersensitivity, or intolerance to [18F]CTT1057, [68Ga]Ga-PSMA-11, or to CT contrast
- 5. Prior and current use of PSMA targeted therapies
- 7a. Prior ADT (first or second generation), including LHRH analogues (agonists or antagonists), within 9 months before screening
- 8. Any 5-alpha reductase inhibitors within 30 days before screening
- 9. Use of other investigational drugs within 30 days before screening
- 10. Castration-resistant patients

- 11. Patient with small cell or neuroendocrine PCa in more than 50% of biopsy tissue

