#### **Derivations:**

Time since initial diagnosis to the first injection (in months) = (date of the first injection – date of first prostate cancer diagnosis + 1) / 30.4375

Time from initial diagnosis to biochemical recurrence diagnosis (in months) = (biochemical recurrence diagnosis - date of first prostate cancer diagnosis + 1) / 30.4375

Time since biochemical recurrence to the first injection (in days) = date of the first injection – biochemical recurrence + 1

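### Year-only diagnosis and recurrence dates default to 01-Jan with no order check, so each such date is about 6 months early on average and can give negative baseline intervals

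*SAP*

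**What the plan says.** SAP 5.1.3 covers two dates: "For incomplete date of initial diagnosis of cancer and date of biochemical recurrence diagnosis". If only the day is unknown, "missing day is defaulted to the 15th of the month"; if the month is unknown too, "missing month and day is defaulted to 01-Jan". The section does not bound the imputed date by other known dates, and it gives no rule for a partial date of definitive therapy.

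SAP 2.3.2 summarises four intervals that use these dates: diagnosis to first injection (months), diagnosis to recurrence (months), definitive therapy to recurrence, and recurrence to first injection (days). Three have formulas under Derivations; for example, diagnosis to recurrence is ("biochemical recurrence diagnosis - date of first prostate cancer diagnosis + 1) / 30.4375". Definitive therapy to recurrence is listed without a formula.

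SAP 5.1.2 treats other dates differently. For AE and concomitant-medication start dates and for safety assessment dates, Table 5-1 handles a known year earlier than the "year of study treatment start date then 01JulYYYY". Under Table 5-2, an imputed end date that falls before its start date is reset to the start date.

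Protocol 5.1 lets recurrence after prostatectomy rest on a PSA value "measured at least 6 weeks after RP" plus a confirmatory value.

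**The concern.** One sentence of the SAP uses a near-midpoint for a missing day and an extreme for a missing month. No reason is given. An imputed 01-Jan can never be later than the true date, so the error in the imputed date has one sign and does not average out across participants.

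Recurrence can be declared within weeks of surgery, so diagnosis, prostatectomy and recurrence can all fall in one calendar year. With no order check, a recurrence known only by that year is then dated before the events it must follow.

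At stake is the description of the recurrence population to which the diagnostic results will be applied: how long participants had had the disease, how soon they relapsed, and how long they waited before the scan.

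**Working it through.** The plan states no figure on this point, so there is none to reproduce. The check is date arithmetic.

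**Inputs.** The default is 01-Jan (SAP 5.1.3). A month is 30.4375 days (SAP 2.1.1, Time unit). The interval formulas are those in SAP 2.3.2. Assumption: the true date is uniform over the recorded year.

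**Error per year-only date.** In a 365-day year, the true date minus 01-Jan takes the values 0 to 364.
- 01-Jan: mean = 364/2 = 182 days; 182/30.4375 = 5.98 months. In a leap year the mean is 182.5 days (6.00 months).
- 01-Jul: the error runs from -181 to +183 days, with mean (183 - 181)/2 = 1 day (0.03 months). The mean absolute error falls from 5.98 to 3.00 months.

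**Effect on each interval when one end is year-only.**

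| Interval | Year-only date | Mean effect |
|---|---|---|
| Diagnosis to injection | Diagnosis | +6.0 months |
| Recurrence to injection | Recurrence, in a year before injection | +182 days |
| Definitive therapy to recurrence | Recurrence | -6.0 months |
| Diagnosis to recurrence | Diagnosis | +6.0 months |
| Diagnosis to recurrence | Recurrence | -6.0 months |

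Two cases differ:
- **Both diagnosis and recurrence year-only.** In different years, the two errors cancel on average. In the same year both become 01-Jan, and the formula returns 1 day.
- **Recurrence and injection in the same year.** If recurrence is uniform up to injection day k of the year, the mean excess is (k - 1)/2. That is 45 days at k = 91 (about the end of March), 90.5 at k = 182 (about the end of June) and 136.5 at k = 274 (about the end of September).

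**Order failure, illustrative case.** Diagnosis is 10-Feb-2020, prostatectomy 01-Apr-2020 and first injection 01-Oct-2021. True recurrence is 20-Sep-2020, recorded as 2020, so the imputed date is 01-Jan-2020.
- Diagnosis to recurrence: (-40 + 1)/30.4375 = -1.3 months. True value: (223 + 1)/30.4375 = 7.4 months.
- Prostatectomy to recurrence: 91 days before surgery. True value: 172 days after.
- Recurrence to injection: 639 + 1 = 640 days. True value: 376 + 1 = 377 days.

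For a recurrence in the same year as a fully dated diagnosis or surgery, 01-Jan comes first unless that event was itself on 01-Jan (364/365 = 99.7%).

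**Would 01-Jul alone be enough?** No. Take a 3-month gap from diagnosis to recurrence within one year. Diagnosis then lies in the first 9 months, and 01-Jul precedes it in (9 - 6)/9 = 33% of cases. With an injection in the first half of the recurrence year, 01-Jul also falls after the injection. An order check is needed as well.

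**Shift in a reported mean.** With a share f of participants having one year-only end, the shift is f x 5.98 months.

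| Assumed f | Shift in mean (months) |
|---|---|
| 5% | 0.3 |
| 10% | 0.6 |
| 20% | 1.2 |
| 50% | 3.0 |

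**The case against.** The strongest reply is that nothing inferential uses these dates. They do not enter the CLR model or the PPV interval (SAP 2.5.2), the candidate covariates (baseline PSA category and initial therapy, SAP 2.5.6), the subgroups, the analysis sets or the sample size. This stands, and it limits the point to a minor one.

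The order failure also needs several things at once: a recurrence known only by year, in the same calendar year as diagnosis or surgery, with the other date known more fully. Recurrence is an inclusion criterion based on PSA measurements. Protocol 11.2 provides for queries on missing values, and Protocol 11.3 requires full verification of adherence to the eligibility criteria. A year-only recurrence date is therefore probably rarer than a year-only date for an older diagnosis. That makes the failure less likely but does not exclude it, and SAP 5.1.3 plans for incomplete recurrence dates.

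The SAP reports medians and quartiles too, and a few early dates would be expected to move those less than the mean. That also stands.

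A reader might infer that SAP 5.1.3 contradicts Table 5-1. It does not. Table 5-1 covers AE, concomitant-medication and safety assessment dates, and it uses 01-Jul only for years before treatment. For year-only dates in the treatment year it uses the treatment start date or 01-Jan, and for later years 01-Jan. It shows only that the SAP already uses a mid-year default for historical dates.

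**Conclusion.** The concern holds as a minor, descriptive one. Each year-only date is early by about 182 days (6.0 months) on average, if the true date is uniform over the year. A year-only recurrence in the same year as a fully dated diagnosis or prostatectomy gives an impossible interval that nothing in SAP 5.1.3 catches.

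A reader might infer that the reported intervals as a whole are off by 6 months, always in one direction. The documents do not support that. Six months applies to an interval with one year-only end, the sign depends on which end is imputed, and the share of year-only dates is not given. The range of 0.3 to 3.0 months for a mean rests on an assumed share of 5% to 50%. Nor is there any route from these dates to the trial's success criteria.

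**What to change.** In SAP 5.1.3:
- Default a missing month and day to 01-Jul of the recorded year.
- Add an order check: diagnosis not after definitive therapy; recurrence not before diagnosis or definitive therapy; recurrence not after first injection (or informed consent, if the sponsor prefers the tighter bound).
- Where 01-Jul breaks the order, use the midpoint of the part of the recorded year that satisfies it.
- Apply a bound only where the bounding date is known. If diagnosis and recurrence are both partial, impute diagnosis first.

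In the illustrative case, 01-Jul-2020 satisfies every bound, and diagnosis to recurrence becomes (142 + 1)/30.4375 = 4.7 months instead of -1.3 (true 7.4).

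The cost is a few sentences in the SAP and a small programming change before database lock. No new data are needed, and no efficacy output changes. It would help to footnote the number of year-only dates under the baseline table, so that readers can judge how much imputation matters.
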